16.4.2 Relatedness

The investigator will use the following definitions to assess the relationship of the AE to the investigational medical device:

Not related - The cause of the AE is known and the event is not related to the investigational medical device.

Possibly related - There is a reasonable possibility that the event may have been caused by the investigational medical device.

Doc No: 280CLD	
Rev: 01	Date: 24 May 2021
Page 63 of 103	

The AE has a timely relationship to the study procedure(s); however, follows no known pattern of response, and an alternative cause seems more likely or there is significant uncertainty about the cause of the event.

Probably related - It is likely that the event was caused by the investigational medical device.

The AE has a timely relationship to the study procedure(s) and follows a known pattern of response; a potential alternative cause, however, may explain the event.

Related - A related event has a strong temporal relationship and an alternative cause is unlikely.

16.4.3 Outcome

The clinical outcome of the AE or SAE will be characterized as follows:

Death - The SAE CRF must be completed for this outcome (see section 16.5 Expedited Reporting of Serious Adverse Events).

Recovered without sequelae - The subject has recovered with no sequelae from the event

Ongoing - Subject did not recover and symptoms continue

Recovered with sequelae - The subject has recovered but with clinical sequelae from the event

Unknown - The subject outcome is unknown

16.4.4 Treatment or Action taken

The treatment or action taken after the occurrence of an AE or SAE will be reported as:

Interventional Treatment - Surgical, percutaneous or other procedure

Medical Treatment - Medication frequency of administration reduction/interruption or discontinuation, or medication initiated for event

None - No action is taken

[figure not shown]
Doc No: 280CLD

Rev: 01 Date: 24 May 2021

Page 64 of 103

16.5 Expedited Reporting of Serious Adverse Events

Any Serious Adverse Event, and device deficiencies should be reported to Vibrant Ltd. within 24 hours of investigators' knowledge of the event. Investigator should report these events on the appropriate SAE form / Device Deficiencies Form in the eCRF and send the form by fax or e-mail, to the following safety contact person:

If applicable, the investigator should also inform the representative of the appropriate local Ethics Committee, within 24 hours of investigator's awareness of the event. A copy of the report cover letter should be filed within the study file.

The sponsor is responsible for the ongoing safety evaluation of the investigational medical device. The sponsor will promptly notify all concerned investigator(s)/institution(s) and the regulatory authority(ies) of findings that could affect adversely the safety of subjects, impact the conduct of the trial, or alter the Medical Ethics Committee approval/favorable opinion to continue the trial.

The sponsor will expedite the reporting to all concerned investigator(s)/institutions(s), to the EC(s), where required, and to the regulatory authority(ies) of the occurrence of Unanticipated Serious Adverse Device Effects.

16.6 Follow- Up of Unresolved Events

All adverse events should be followed until they are resolved or the subject's participation in the study ends.

Doc No: 280CLD

Rev: 01 Date: 24 May 2021

Page 65 of 103

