7.2 Intended Use

The Vibrant Capsule is an orally administered non-biodegradable vibrating capsule intended to be prescribed for the treatment of adult chronic idiopathic constipation in patients who have not experienced relief of their symptoms from one or more available therapies (used for at least 1 month at recommended dosage) or unable to tolerate these therapies. The capsule achieves its purpose by mechanically inducing a bowel movement in the large intestine.

Doc No: 280CLD

Rev: 01 Date: 24 May 2021

Page 23 of 103

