14.1 Inclusion Criteria

1. Subjects aged 22 years and older.

- 2. Subjects with Chronic Idiopathic Constipation (CIC) according to Rome IV criteria
- 3. Subjects who have not experienced relief of their symptoms from one or more available therapies (for at least one month at recommended dose) or unable to tolerate these therapies.
- 4. Subjects with an average of ≤2.5 Spontaneous Bowel Movements (SBM) per week and ≥1 SBM per week (as a result of at least 1 SBM and not more than 3 SBMs during each of the run-in weeks)
- 5. Subjects above 50 years old or <50 years old and with alarm signs should have colonoscopy performed within 10 years prior to study participation. Colonoscopy results should exclude GI obstruction and/or GI malignancy.
- 6. Subject signed the Informed Consent Form (ICF)
- 7. Female subjects must have a negative blood pregnancy test during screening, confirmed by a negative urine pregnancy test during baseline and must not be lactating prior to receiving study medication. For females of child-bearing potential, a hormonal (i.e., oral, implantable, or injectable) and single-barrier method, or a double-barrier method of birth control must be used throughout the study. All other female subjects must have the reason for their inability to bear children documented in the medical record [i.e., tubal ligation, hysterectomy, or post-menopausal (defined as a minimum of one year since the last menstrual period)]; in these circumstances, a pregnancy test will not be necessary.

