14.2 Exclusion Criteria

- 1. History of complicated/obstructive diverticular disease
- 2. History of intestinal or colonic obstruction, or suspected intestinal obstruction.
- 3. History of significant gastrointestinal disorder, including any form of inflammatory bowel disease or gastrointestinal malignancy (celiac disease is accepted if the subject has been treated and is in remission)
- 4. Clinical evidence of current and significant gastroparesis
- 5. Use of any of the following medications:

Doc No: 280CLD

Rev: 01 Date: 24 May 2021

Page 45 of 103

• Medications that may affect intestinal motility (including but not limited to prokinetics, anti-Parkinsonian medications, opiates, opioids, Verapamil, Nifedipine, iron, magnesium supplements, Tricyclic antidepressants (TCAs), Heparin, Warfarin and Baclofen.

- With the exception of antidepressants (other than TCAs), thyroid or hormonal replacement therapy, when the subject has been on a stable dose for at least 3 months prior to enrollment.
- 6. Clinical evidence of significant respiratory, cardiovascular, renal, hepatic, biliary, endocrine, psychiatric or neurologic disease.
- 7. Presence of cardiac pacemaker, gastric electrical stimulator or any electrical implanted device.
- 8. History of, or current eating disorders, such as anorexia, bulimia, or compulsory overeating.
- 9. Diagnosis of mega-rectum or colon, congenital anorectal malformation, clinically significant rectocele, history of intestinal resection (with an exception for appendectomy, cholecystectomy and inguinal hernia repair), history of bariatric surgery or evidence of any structural abnormality of the gastrointestinal tract that might affect capsule's transit.
- 10. History of Zenker's diverticulum, dysphagia, esophageal stricture, eosinophilic esophagitis or achalasia
- 11. Chronic use of non-steroidal anti-inflammatory drugs (NSAIDs): chronic use is defined as taking full dose NSAIDs more than three times a week for at least six months. Subjects on cardiac doses of aspirin may be enrolled in the study.
- 12. Subjects with pelvic floor dysfunction/defecatory disorder, based on subject history.
- 13. Participation in another interventional clinical study within one month prior to screening.
- 14. Women who are pregnant or lactating
- 15. Use of any medication for constipation relief during the study, except as rescue medication, as indicated by study rules.

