22. INFORMED CONSENT

Written informed consent must be obtained from each study subject. The subject will be asked to read the informed consent form and to sign the form to indicate consent to participate in the study.

The investigator will explain carefully to the subject the research nature of the study. The scope and aims of the research will be described together with known or foreseeable benefits, risks and discomforts that subjects may experience. Appropriate alternative treatments will be discussed so that the subject may determine whether or not he or she wishes to participate in the study. The subject must understand that throughout the study his or her participation remains voluntary and protected by the Declaration of Helsinki. The investigator is responsible for obtaining written (or witnessed) informed consent from potential subjects prior to study entry. The task of obtaining informed consent can be delegated, per PI discretion. Subjects will be given time to read the informed consent and ask any questions before being asked to sign the form. The informed consent (approved by the sponsor and the Ethics Committee) must be signed and dated by the subject and the investigator (or investigator's designee). One copy of the signed consent will be given to the subject, a second copy will be sent to the referral investigator and the original will be retained by the investigator. Subject should be identified during screening visit by driving license or any other identity card.

Subjects may withdraw their consent to participate in the study at any time without prejudice. The investigator may withdraw a subject if, in his clinical judgment, it is in the best interest of the subject or if the subject cannot comply with the protocol. Attempts should be made to complete any examinations and the sponsor must be notified of all withdrawals.

Should a protocol amendment be made, the subject's consent form may be revised to reflect the changes of the protocol. It is the responsibility of the investigator to ensure that an amended informed consent is approved or reviewed by the EC/IRB, and that it is signed by all subjects subsequently entered in the study and those currently in the study, if affected by the amendment.

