28. SUBJECT / STUDY DISCONTINUATION

Page 81 of 103

Subjects should be removed from the study whenever considered necessary for their welfare or when the subject expresses a desire to withdraw from the study. Non-compliance with the protocol, the occurrence of a Serious Adverse Event or any medical condition that, in the opinion of the investigator, warrants discontinuation from the study for the safety of the subject, may necessitate discontinuing a subject. If a subject is discontinued, the reason must be entered on the case report form and signed by the investigator. In case of any questionable situation, the study monitor or Vibrant Ltd. personnel should be consulted. When a subject is removed from the study as a result of Serious Adverse Event, a final physical examination must be performed. Subjects removed from the study because of an adverse event will be followed-up until the adverse event has been resolved.

In the case that the occurrence of adverse events is greater than anticipated, the clinical investigation will be suspended; in such a case, a safety committee will be arranged to decide if the study could be continued. The Ethics Committee will be notified and the results of the safety committee discussions will be brought for the EC/IRB review and decision.

Early termination could be a result of:

- 1. Withdrawal of informed consent by the subject.
- 2. Subjects who after inclusion develop medical diseases which may affect the function and interpretation of study results.
- 3. Serious protocol deviation.
- 4. Non-compliance with medical device administration or study procedures as determined by the sponsor.
- 5. Change in subject's condition.
- 6. Subject is Lost to follow-up.
- 7. Confirmed pregnancy.
- 8. Regulatory authorities stop the trial.

During the study, subjects exiting the trial will be replaced with new subjects, up to 10%

Site staff should set an early termination visit as soon as they become aware of subject's discontinuation. During this visit, any remaining study supplies should be collected and accountability should be conducted if applicable. 'End of study' from should be completed in source documents and any other relevant information should be documented (for example, in case of AE).

Doc No: 280CLD

Rev: 01 Date: 24 May 2021

Page 82 of 103

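### Section 16.6 ends follow-up of open serious and device-related adverse events at study exit unless the event caused removal, and no later safety contact is scheduled

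*Combined protocol and SAP*

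**What the plan says.** The general rule is the single sentence of section 16.6: "All adverse events should be followed until they are resolved or the subject's participation in the study ends". It makes no distinction by seriousness or relation to the device.

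Section 28 contains the one exception found: "Subjects removed from the study because of an adverse event will be followed-up until the adverse event has been resolved". Removals for a serious event also require a final physical examination. For all early exits, section 28 adds "Site staff should set an early termination visit as soon as they become aware of subject's discontinuation", and adverse events are among the things that may be documented there. On withdrawal, section 22 adds: "Attempts should be made to complete any examinations and the sponsor must be notified of all withdrawals".

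Section 16.4.3 allows an event to be recorded with the outcome Ongoing. Section 16.5 sets a 24-hour deadline for reporting serious events, counted from the investigator's knowledge of them. It does not say how long an event is followed.

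Participation is scheduled to end at Visit 4 (section 15.11, day 56 ± 2), which is also the last column of Table 1 (section 15.18). The phone-call row of that table is on an as-needed basis throughout.

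**The concern.** Length of follow-up depends on why the subject leaves, not on how serious the event is or whether the device may have caused it. A mild event that leads to removal must be followed until it resolves. A serious event still open when a subject completes Visit 4 need not be.

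The protocol's own definitions call for later information. Section 16.2 judges whether a serious device effect is unanticipated partly by its outcome, and counts permanent impairment as a seriousness criterion. Section 16.4.3 separates recovery with sequelae from recovery without. None of these can be settled for an event that is dropped while open.

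The device is an "orally administered non-biodegradable vibrating capsule", and exclusion criterion 9 bars "evidence of any structural abnormality of the gastrointestinal tract that might affect capsule's transit". The sponsor thus treats passage of the capsule as relevant to who may enrol, so it is reasonable to ask how soon after the last capsule planned safety observation stops.

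At stake are the outcome or worsening of a serious or device-related event open at exit, and any event that begins shortly after the last visit. Events that begin before exit are still counted in the section 17.9.7 tables.

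**Working it through.** **Step 1. The rules by route of exit.**

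| Situation at exit | Governing text | Follow-up required |
|---|---|---|
| Completes Visit 4, event open | 16.6, 16.4.3 | Ends at Visit 4; may be closed as Ongoing |
| Removed because of an adverse event | 28 | Until resolved; a serious event also brings a final physical examination |
| Leaves for another reason, event open | 28 (early termination visit), 22, 16.6 | Ends with participation; may be closed as Ongoing |
| Event begins after exit | 16.5, if serious and the investigator learns of it | No scheduled contact to detect it |

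Only the second row gives follow-up beyond exit. Seriousness and device relation change nothing in the first and third rows.

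**Step 2. Time from the last scheduled capsule to Visit 4.**

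Inputs: 16 capsules, the first on site on day 0 and the rest on Mondays and Thursdays (15.9); Visit 4 on day 56 ± 2, so day 54 to 58 (15.11). For Tuesday, Wednesday and Friday starts, 15.9 names the day of the second capsule. For Monday and Thursday starts I take the next regular dosing day. From capsule 2 to capsule 16 there are 14 further doses at two per week, which is 7 weeks or 49 days.

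Day of capsule 16 = day of capsule 2 + 49. Gap = day of Visit 4 − day of capsule 16.

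| Baseline weekday | Capsule 2 (day) | Capsule 16 (day) | Gap, visit on day 54 | Day 56 | Day 58 |
|---|---|---|---|---|---|
| Monday | 3 | 52 | 2 | 4 | 6 |
| Tuesday | 2 | 51 | 3 | 5 | 7 |
| Wednesday | 5 | 54 | 0 | 2 | 4 |
| Thursday | 4 | 53 | 1 | 3 | 5 |
| Friday | 3 | 52 | 2 | 4 | 6 |

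Planned observation after the 16th capsule is 2 to 5 days when the visit is on day 56, and 0 to 7 days over the whole window.

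**Step 3. Where a later call would fall.**

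A call 7 to 14 days after a day-56 visit comes 2 + 7 = 9 to 5 + 14 = 19 days after the 16th capsule. Over the visit window the range is 0 + 7 = 7 to 7 + 14 = 21 days.

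The plan states no figure on this point that could be reproduced. The documents give no rate of events open at exit or of late events, so the number of subjects affected cannot be computed.

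**The case against.** The strongest reply is that the gap is narrow. A serious event may itself lead to discontinuation, which brings in section 28's follow-up to resolution. Serious-event removals get a physical examination, and early exits get a visit. Section 16.5 makes the sponsor responsible for continuing safety evaluation of the device and puts no end date on serious-event reporting. Remaining capsules are collected at Visit 4, so dosing does not go on. The anticipated events in section 16.3 are mostly gastrointestinal symptoms, and section 17.9.7 does not tabulate outcome. All of this stands. It reduces the gap to subjects who complete, or leave for other reasons, with an open serious or device-related event, and to events that begin after exit. It does not close it, because after exit the sponsor depends on the site happening to hear.

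A reader might go further and infer that the last capsule is often still in the gut when observation ends. Inclusion criterion 4 requires an "average of ≤2.5 Spontaneous Bowel Movements (SBM) per week and ≥1 SBM per week", which is a mean spacing of 7/2.5 = 2.8 days to 7/1 = 7 days, against a gap of 0 to 7 days. The documents do not support that inference:

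- Spontaneous movements exclude those within 48 hours of laxative or rescue use and those with digital help, yet a capsule can pass with either. Rescue is allowed after 3 days without a movement.
- The interval between movements is not a transit time.
- A mean is not a maximum. One movement on day 1 of the first run-in week and one on day 7 of the second meet the criterion with a 13-day interval.
- Most of section 9.1 and sections 10 and 11 cannot be seen. Transit data or a capsule-retention rule may be there.

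A reader might also treat pregnancy as part of this point. Section 28 lists "Confirmed pregnancy" as a possible reason for early termination, fetal harm is a seriousness criterion in section 16.2, and the visible text has no rule for following a pregnancy to its outcome. That is a statement about absence in a document with unseen pages, and entry requires negative tests and contraception. It is a separate and optional matter.

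**Conclusion.** The point holds for the follow-up rule. As written, section 16.6 lets a serious or device-related event that is open at exit go without an outcome unless it was the reason for removal, and no scheduled contact would pick it up later. Confidence in that reading is high, because the sections on follow-up, schedule and discontinuation are legible.

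The timing result, 0 to 7 days from the 16th scheduled capsule to Visit 4, assumes that all capsules are taken on the section 15.9 calendar. It shows how short planned observation is after the last dose. It does not show that a capsule is retained or that harm follows.

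The change should be made as an inexpensive improvement to patient safety and to the safety data. It does not bear on the primary or secondary efficacy results, and nothing in the documents suggests that the loss of information would differ between arms.

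**What to change.** Amend section 16.6 so that any serious or device-related event open at exit is followed until it has resolved or is stable, whatever the reason for exit. Add a cross-reference that leaves section 28's rule for adverse-event removals unchanged.

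As a low-cost addition, put one fixed safety call in Table 1 about 7 to 14 days after Visit 4 or the early termination visit, to record new events and the status of open ones. The window is a practical choice and is not derived from transit data. If the sponsor holds such data, they should set the window.

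Cost: protocol wording, about 102 calls at the planned size and at most 250 at the section 17.5.3 ceiling, and a final database lock later by about the call window. Open events that need longer follow-up can be reported as safety updates outside the lock. State that the interim soft lock in section 17.5.1 does not wait for the calls.

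Optionally, and after checking the unseen pages, add a separate provision to follow any in-study pregnancy to its outcome. That would take longer than a single call.

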17. STATISTICAL CONSIDERATIONS

17.1 Study Design and Objectives

The study is planned as a prospective, randomized, multi-center, double-blinded, placebo-controlled, 2 arm study, designed to assess the efficacy and safety of Vibrant capsule vs. placebo, for the treatment of chronic idiopathic constipation.

After a run-in period of 14-28 days, subjects will be randomized with a ratio of 1:1 to either Vibrant capsule or placebo capsule. The subjects will then be treated with the active Vibrant or placebo capsule for 8 weeks. The first 2 weeks of treatment will be considered as a subjects' training period. One interim analysis will be conducted after about 80 evaluable subjects will complete 8 weeks of treatment.

17.2 Study Endpoints

17.2.1 Primary Efficacy Endpoint

There are two primary efficacy endpoints for this study.

The two primary efficacy endpoints are the CSBM1 success rate, defined as an increase from the run-in period of at least one weekly Complete Spontaneous Bowel Movement (CSBM) during at least 6 of the 8 weeks of treatment, and CSBM2 success rate, defined as an increase from the run-in period of at least two weekly Complete Spontaneous Bowel Movement (CSBM) during at least 6 of the 8 weeks of treatment.

The study will be deemed successful if either the CSBM1 or the CSBM2 success rate is statistically significantly higher in the active arm, than in the placebo arm.

Doc No: 280CLD Rev: 01 Date: 24 May 2021

Page 66 of 103

17.2.2 **Secondary Efficacy Endpoints**

Secondary efficacy endpoints include:

- Change from baseline in average straining. 1.
- 2. CSBM1 expanded success rate, defined as an increase from the run-in period of at least one weekly Complete Spontaneous Bowel Movement (CSBM) during at least 5 of the 8 weeks of treatment.
- Change from baseline in average stool consistency, using the Bristol Stool Scale 3.
- 4. CSBM2 expanded success rate, defined as an increase from the run-in period of at least two weekly Complete Spontaneous Bowel Movement (CSBM) during at least 5 of the 8 weeks of treatment
- 5. Change from baseline in average bloating.

17.2.3 **Additional Efficacy Endpoints**

Additional efficacy endpoints include:

- SBM success rate, defined as an increase from baseline at least one weekly spontanuous Bowel Movement (SBM) during at lease 6 out of 8 weeks of treatment.
- Incidence of Rescue Medication use during the treatment period.
- Change from baseline in weekly number of Spontaneous Bowel Movement (SBM).
- Change from baseline in weekly number of Complete Spontaneous Bowel Movement (CSBM).
- Rate of SBM < 24 hours after first dose
- Change from baseline in average abdominal gas.
- Change from baseline in average abdominal pain.
- Change from baseline in abdominal discomfort.
- Time to occurrence of spontaneous bowel movement after first capsule activation.
- Change from baseline in quality of life using the PAC-QOL (Patient Assessment of Constipation Quality of Life) questionnaire.

